5.3 Rationale for the Selection of Study Endpoints

5.3.1 Primary Endpoint

The primary endpoint of this trial will be the proportion of patients who achieve $a \ge 50\%$ decline in serum PSAafter 12 weeks of protocol therapy, which can serve as a marker of biological activity of itraconazole in biochemically relapsed hormone sensitive prostate cancer. Although decline in serum PSA has not been prospectively validated as a surrogate marker for clinical outcomes in this disease setting, a prior retrospective analysis identified PSA decline on therapy as an independent predictor of prostate-cancer mortality in patients with biochemically relapsed prostate cancer treated with androgen deprivation therapy [35]. In addition, PSA decline was chosen as the primary endpoint in several prior trials of non-hormonal agents with varying mechanisms of actionin this disease setting, including studies investigatingthe small molecule tyrosine kinase inhibitorimatinib and immune-modulating therapy with GM-CSF [12, 15]. Furthermore, PSA decline on therapy as a primary endpoint may be less prone to inter-patient variability than other endpoints involving PSA modulation such as time to PSA progression or change in PSA doubling time, as has been observed in prior trials of non-hormonal therapies in biochemical relapse [14].

Favorable results with respect to decline in PSA, along with acceptable safety and endocrinologic data, would form the basis for further study of itraconazole in biochemically relapsed disease, with the larger subsequent studies adequately designed (with sufficient power) for primary efficacy endpoints of clinical relevance, including time to first metastasis and overall survival.

5.3.2 Secondary Endpoints

A number of additional endpoints will be evaluated to assess the overall impact of itraconazole on PSA kinetics, clinical outcome, safety, and pharmacokinetics.

5.3.2.1 PSA Kinetics

Mean Change From Baseline in PSADT

The mean change from baseline in PSADT after 12 weeks of protocol therapy will be measured for patients treated with itraconazole. A prior retrospective analysis of four non-hormonal agents tested in the biochemically relapsed setting identified change in the pre-treatment vs. on-treatment natural log PSA slope as an independent prognostic factor with respect to development of metastatic disease [37]. Novel agents tested in BCR may have clinical benefit without causing PSA decline but by slowing the rate of PSA rise instead, especially for agents with a cytostatic effect on tumor cells. It is not known if itraconazole has either cytocidal or cytostatic activity (or neither) in biochemically relapsed prostate cancer, and thus measuring both declines in PSA and changes in PSA kinetics is warranted.

Time to PSA Progression

The PCWG2 has suggested that duration of clinical activity is a key intermediate endpoint in initial phase II trials of agents conducted in the BCR disease population [36]. Indeed, in an exploratory analysis of a trial of IADT in BCR patients, Yu and colleagues demonstrated that in patients who completed the first cycle of IADT, a shorter duration of the first "off treatment" interval was associated with a shorter time to developing castrate resistant prostate cancer and shorter overall survival [41]. In the proposed trial, the median time to PSA progression on itraconazole therapy will be evaluated. The definition of PSA progression, as outlined in Section 2 (> 50% and >2 ng/mL above nadir (or above baseline if no PSA decline), is acknowledged to be arbitrary but does reflect PCWG2 guidelines for PSA progression in the castrate-resistant disease setting.

Given the heterogeneity of the study populations in prior studies of non-hormonal agents evaluated in BCR, as well as the variable definition of PSA progression used in prior clinical trials, using historical data to generate accurate estimates of median time to PSA progression is problematic. The analysis in the current study is exploratory in nature, aimed at generating preliminary estimates of the impact of itraconazole on the time to PSA progression.

5.3.2.2 Clinical Outcome

The median time to clinical progression, as defined by the first occurrence of either initiation of non-protocol therapy (including initiation or resumption of ADT) or development of overt

metastatic disease, as well as the median metastasis-free survival, will be determined for patients treated with itraconazole. As was the case for time to PSA progression, this analysis is exploratory in nature, and the aim is to generate preliminary estimates of time to disease progression to potentially aid in the planning of future study of itraconazole in biochemically relapsed prostate cancer. Serial radiographic scans will not be mandated by the study, as this does not reflect standard clinical practice (see Section 6). Scans will be required at baseline, at the time of PSA progression, and as clinically indicated for signs/symptoms on history and physical exam. If itraconazole is further evaluated in a definitive, placebo-controlled phase II/III trial in BCR, periodic scans would need to be mandated to ensure balanced evaluations per treatment arm.

5.3.2.3 Pharmacokinetics

The mean steady-state serum concentration of itraconazole and hydroxyl-itraconazole, its major active metabolite, will be measured after 4 weeks of protocol therapy. Prior studies have demonstrated variability in the oral bioavailability of the oral capsule formulation, dependent mostly upon the degree of gastric acidity (lower pH enhances oral absorption) at the time of ingestion. In an exploratory analysis of low- and high-dose itraconazole in CRPC, higher steady-state serum concentrations of itraconazole and hydroxyl-itraconazole were associated with a higher likelihood of being free of PSA progression at 24 weeks and displaying greater percentage PSA decline on therapy [31]. A similar analysis will be carried out in the current study.

5.3.3 Correlative Endpoints

5.3.3.1 Endocrine Parameters

The mean change from baseline in serum androgen levels, including testosterone, DHEA-S, and androstenedione after 12 weeks of therapy with itraconazole will be determined to investigate further the mechanism of action of itraconazole in prostate cancer. Prior study in CRPC provided preliminary evidence that itraconazole, unlike the related azole compound ketoconazole, has a mechanism of action distinct from androgen synthesis inhibition [19], albeit in a castrate patient population. Demonstrating in the current study, with a non-castrate patient population, that itraconazoletherapy concurrently does not significantly impact serum androgen levels yet modulates serum PSA will lend further support to the hypothesis that itraconazole has a mechanism of action distinct from ketoconazoleand androgen synthesis inhibition. The main limitations of this particular analysis is that serum hormone levels may not reflect intra-tumoral androgen concentrations, and that this patient population is non-castrate with a different systemic hormonal milieu than the previous study in CRPC.

In the prior clinical trial of itraconazole in CRPC, there were several patients with a constellation of adverse events including hypokalemia, hypertension, and peripheral edema [19]. This constellation of symptoms has also occasionally been observed in prior studies of high dose itraconazole in patients with chronic fungal infections, and raises the possibility of induced mineralocorticoid excess. Serum aldosterone levels were measured in the prior study of itraconazole in CRPC (and were not elevated on therapy); however upstream compounds within

the adrenal synthetic pathway with mineralocorticoid activity, including deoxycorticosterone (DOC) and 11-deoxycortisol were not measured. A more comprehensive panel of adrenal and pituitary hormones, including ACTH, DOC, aldosterone, and 11-deoxycortisol, will be measured on a serial basis in the current study and the mean change from baseline will be determined.

Evaluation for a relationship between baseline and percent change in serum hormone levels with PSA modulation will be evaluated in the current study. Prior studies of ketoconazole and abiraterone in metastatic CRPC demonstrated a relationship between higher baseline levels of adrenal androgen levels with clinical response [21, 42], and a prior trial of estrogenic compounds (DES and the herbal supplement PC-SPES) in CRPC demonstrated that a decline adrenal androgen DHEA-S was related to a decline in serum PSA on therapy [43]. Whether the same relationships apply to itraconazole, which is hypothesized to have a mainly non-hormonal mechanism of action, and whether the same relationships between serum hormone levels and clinical response apply to the biochemically relapsed disease setting as it does in CRPC, will be evaluated in the current study.

5.3.3.2 Hedgehog Pathway

The impact of itraconazole on Hedgehog pathway activity will be assessed by serial skin biopsies obtained at baseline and after 4 weeks of therapy. Hedgehog pathway activity will be assessed by quantitative reverse transcriptase-polymerase chain reaction (RT-PCR) analysis of *GLI1*mRNA transcripts in the skin biopsy specimens. *GLI1* is a downstream transcription factor upregulated by activation of the Hh pathway that functions in a positive feedback loop. This method for analysis of Hh pathway activity has been previously validated in a study of the small molecule *SMO* inhibitor GDC-0449 in basal cell carcinoma of the skin [25]. In patients with CRPC treated with itraconazole, down-regulation of *GLI1* expression was shown to be associated with a longer PSA progression- free survival [31].

In an exploratory fashion, for patients with prior archived primary prostate cancer tissue available, the relationship between mRNA andimmunohistochemical expression of components involved in the Hh pathway, including Sonic hedgehog ligand, *PCTH1*, *GL11*, and *SMO*, and PSA modulation on subsequent itraconazole therapy will be determined. Such an analysis may eventually lead to the development of a predictive biomarker for itraconazole, which would require prospective validation in larger placebo controlled trials.

In summary, the proposed trial will evaluate the effects of itraconazole in patients with nonmetastatic biochemically relapsed prostate cancer with a variety of biologically relevant endpoints. Favorable results with respect to PSA modulation, along with acceptable toxicity and lack of adverse impact on endocrine parameters, along with demonstration of Hedgehog pathway down-regulation, would demonstrate itraconazole as a viable non-castrating treatment strategy in this disease setting, and may help to form the justification for a larger placebo-controlled clinical trial of itraconazole in BCR, with primary endpoints potentially including time to metastatic disease and overall survival.

6.1 Study Schedule

	Pre-Study	Cyc	cle 1	Cycle 2	Cycle 3	Cycle 4	Cycle 5 and beyond	End of Study
Procedure	Screening	Day 1	Day 8 (+/- 3 days)	Day 1 (+/- 7 days)	PSA or Clinical Progression			
Informed Consent ^a	Х							
Within 3 months of Cycle Day	y 1		1	1	1		1	
PSA ^b	X °	Х		Х	Х	Х	Х	Х
Serum Testosterone ^d	X ^e			Х		Х		Х
Within 6 weeks of Cycle Day	1						•	
Whole body bone scan + CT or MRI of and/pelvis ^f	Х							X ^g
Skin biopsy (optional) ^h	Х			Х				
Within 28 days (4 weeks) of C	ycle Day 1							
Demographics	Х							
History / Physical	Х	Х	Х	Х	Х	Х	Х	
Height/Weight	Х	Х	Х	Х	Х	Х	Х	
ECOG Performance Status	Х	X	X	Х	Х	Х	Х	
Toxicity Assessment	Х	Х	Х	Х	Х	Х	Х	Х
CBC w/diff and platelets	Х						Х	
BUN / Creatinine	Х						Х	
ALT, AST, AlkP, total bilirubin	Х		X	Х	Х	Х	Х	
Other serum hormones ^d	Х			Х		Х		Х

6.1 Study Schedule

	Pre-Study	Cycl	e 1	Cycle 2	Cycle 3	Cycle 4	Cycle 5 and beyond	End of Study
Procedure	Screening	Day 1	Day 8 (+/- 3 days)	Day 1 (+/- 7 days)	PSA or Clinical Progression			
Plasma/serum for banking (optional) ⁱ	Х			Х		Х		Х
PBMCs for banking (optional) ⁱ	Х							
Concomitant Medications	Х	Х	Х	Х	Х	Х	Х	
Serum sodium and potassium	Х		Х	Х	Х	Х	Х	
Archived primary prostate cancer tissue (optional) ^j	Х							
Itraconazole dispensed ^k		Х		Х	Х	Х	Х	
After Cycle 1								
Trough itraconazole& [OH]- itraconazole serum levels ¹				Х				

^a Informed Consent prior to any Screening procedures

Measured in same laboratory at each time point during study (if possible).

^c All serum PSA measurements within 3 months prior to Day 1 of protocol therapy will be included for the calculation of baseline PSA doubling time, with a minimum of three values each spaced at least 14 days apart.

^d Serum hormone levels should be collected between 8:00 am and 12:00pm if possible; will be shipped to UCSF and banked for later analyses; includes testosterone, cortisol, aldosterone, deoxycorticosterone, 11-deoxycortisol, adrenocorticotropic hormone (ACTH), dihydroepiandrostenedione-sulfate (DHEA-S), and androstenedione (see Appendix 3, section IV for processing, storage, and shipping instructions).

^e For serum testosterone measurement, if the patient does not have a history of ADT, a single measurement > 150 ng/dL within 3 months prior to Day 1 of protocol therapy will be required for study entry. For patients with any prior history of ADT, the two most recent serum testosterone measurements prior to Day 1 of protocol therapy must fulfill the following requirements:

- Both measurements > 150 ng/dL
- Both measurements obtained within 3 months prior to day 1 of protocol therapy
- Measurements must be spaced at least 14 days apart
- There must not be an increase of > 50 ng/dL between the two consecutive measurements
- ^f IV contrast with CT or MRI per individual investigator discretion. Whole body bone scan may consist of either technetium-99 labeled scan or sodium-fluoride PET bone scan.
- ^g May be omitted if completed within the past 30 days.
- ^h 3 mm punch biopsy non-scalp skin containing hair follicles

¹ Collection of PBMCs at baseline and serum/plasma at baseline, cycle 2 day 1, cycle 4 day 1, and at disease progression is optional. Blood will be shipped to UCSF and stored within HDFCCC Tissue Bank. See appendix 3, section IV for processing and shipping instructions).
6.1 **Study Schedule**

	Pre-Study	Cycl	e 1	Cycle 2	Cycle 3	Cycle 4	Cycle 5 and beyond	End of Study
Procedure	Screening	Day 1	Day 8 (+/- 3 days)	Day 1 (+/- 7 days)	PSA or Clinical Progression			

j

Archived formalin-fixed paraffin embedded prostate biopsy or prostatectomy specimen (optional) Itraconazole to be taken as three (100 mg) capsules twice daily with food (6 capsules total per day; 168 capsules dispensed every 4 weeks during study visits) k

1 Hold am dose of itraconazole

ALT = alanine aminotransferase, AST = aspartate aminotransferase, AlkP = alkaline phosphatase, PBMC = peripheral blood mononuclear cells

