6.3.5 Laboratory/Radiographic Assessment

The frequency and schedule of laboratory and radiographic assessment is outlined above in the study schedule. Serum PSA will be measured on a monthly basis while patients are receiving protocol therapy. A whole body bone scan (either Na-F PET or technetium-99 bone scan), along with cross-sectional imaging of the abdomen/pelvis (CT or MRI) will be obtained at baseline and at the time of PSA or clinical progression, whichever occurs first.

Liver function tests and serum sodium and potassium levels will be measured pre-study, on day 8 +/- 3 days, day 28 +/- 7 days, then every 4 weeks +/- 7 days thereafter. BUN/serum creatinine will be measured pre-study and every 4 weeks +/- 7 days.

Serum itraconazole and hydroxy-itraconazole levels will be measured at the day 28 (+/- 7 days) study visit. Hormone levels (outlined above in the study schedule) will be measured at baseline, day 28 (+/- 7 days), and week 12 (+/- 7 days) of protocol therapy.

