Bioavailability: Variable, ~30-40%% (capsule). *Half-life elimination:* Oral: Single dose: ~21 hours, steady state: 64 hours; Cirrhosis (single dose): 37 hours (range 20-54 hours) *Time to peak, plasma:* 3-5 hours *Excretion:* Urine (<0.03% active drug, 40% as inactive metabolites); feces (~3% to 18%)

Storage and Handling: Itraconazole capsules are supplied in HDPE bottles of 30. They should

be stored at room temperature (15-30 degrees Celsius) and protected from light and moisture.

Dose: 300 mg PO BID. Three 100 mg capsules taken twice daily with food (6 capsules per day in total).

Possible Anticipated Adverse Events: The most frequently reported adverse events in prior clinical trials of itraconazole were gastrointestinal in nature, including diarrhea, nausea and/or vomiting, anorexia, or abdominal pain. Other potential adverse events include peripheral edema, hypertension, hypokalemia, fatigue, and elevated liver enzymes. Rare but serious and potentially life threatening adverse events include adrenal insufficiency, allergic reactions including Stevens-Johnson syndrome, congestive heart failure, and liver failure. Itraconazole may also potentially interact with a number of other medications and herbal supplements, so a careful review of the concurrent medications is warranted during therapy (see Appendix 2 for list of potential interacting medications to avoid while on itraconazole therapy).

Dispensing of Drug: A 28 day supply of study drug will be provided to patients at each study visit every 4 weeks.

Inventory and Control: The itraconazoleused for this study must be maintained under adequate security and stored in the pharmacy at the study site until dispensing or their return to the UCSF Helen Diller Family Comprehensive Cancer Center investigational pharmacy. Investigators may not supply study medication to any person not enrolled in this study or to any person not named as a sub-investigator.

In addition, the investigator must maintain an accurate, running inventory of all drug supplies received and dispensed during conduct of the study. At the completion of the study, a copy of the final inventory will be supplied to the UCSF Helen Diller Family Comprehensive Cancer Center investigational pharmacy. The original will be retained by the investigator in the study files.

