8.3 Dose Modification for Other Adverse Events

For adverse events of grade 1 in severity, treatment will be per institutional guidelines, and no dose interruption will be mandated. For adverse events of grade 2 in severity that the study investigator deems as possibly, probably or definitely related to study drug, treatment will be interrupted until the adverse event resolves to grade ≤ 1 in severity, at which point itraconazole will be re-started at a reduced dose of 400 mg/day. If a patient experiences a recurrent adverse event of grade 2 in severity, itraconazole will be held until the adverse event resolves to grade ≤ 1 in severity, at which point itraconazole will be held until the adverse event resolves to grade ≤ 1 in severity, at which point itraconazole will be held until the adverse event resolves to grade ≤ 1 in severity, at which point itraconazole will be re-started at 200 mg/day.

Treatment will be interrupted for grade 3 adverse events that study investigator attributed as possibly, probably, or definitely related to study medication. Treatment will be held until the adverse event resolves to grade ≤ 1 in severity, at which point therapy will be re-instituted at a reduced dose of 200 mg/day. If the adverse event recurs to grade 2 in severity, treatment will be held until the adverse event resolves to grade ≤ 1 in severity, at which point therapy will be re-instituted at 200 mg/day per individual investigator discretion. If the adverse event recurs to grade 3 or higher in severity, treatment will be permanently discontinued and patients will not be re-challenged for any grade 4 adverse events occurring while receiving protocol therapy.

Grade of Other AE	Action	Further Action/Maintenance
1	Treatment per institutional guidelinesNo dose interruption will be mandated	None
2	 Treatment interrupted until the adverse event resolves to grade ≤ 1 in severity @ ≤ 1 in severity, re-start itraconazole at reduced dose of 400 mg/day 	 If recurrent grade 2 AE, hold itraconazole until resolves to grade ≤ 1 in severity @ ≤ 1 in severity, re-start itraconazole at reduced dose of 400 mg/day

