9.4 Serum Drug Levels

The plasma trough concentrations of itraconazole and hydroxyitraconazole will be assessed by a validated liquid chromatography-mass spectrometry assay developed by the Analytical Pharmacology Core Laboratory at Johns Hopkins University. Trough levels will be drawn after 4 weeks of protocol therapy, collected before the morning dose of itraconazole. Patients should hold their morning dose until the collection is completed.

Patients will have about 5 ml of blood collected into tubes containing K2-EDTA as an anticoagulant (lavender top). Following extraction, blood will be immediately placed on ice or refrigerated until processed. The actual day and time of collection will be recorded. Plasma will be separated from whole blood as soon as possible following extraction. This will be done by centrifuging whole blood at 1000 x g for 10 minutes at 4°C. Plasma will then be transferred to a screw-cap polypropylene cryotube for determination of itraconazole and hydroxyitraconazole concentrations. The polypropylene tube will be labeled with patient''s initials, study number, day, time, and protocol day and then frozen at -70° C until the time of analysis (see appendix 3 for additional information regarding processing and shipping instructions).

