The protocol, the proposed informed consent form, and all forms of participant information related to the study (e.g. advertisements used to recruit participants) will be reviewed and approved by the Committee on Human Research (UCSF"s IRB). Prior to obtaining CHR approval, the protocol must be approved by the Helen Diller Family Comprehensive Cancer Center Protocol Review Committee (PRC). The initial protocol and all protocol amendments must be approved by the IRB prior to implementation.

Informed Consent

All participants must be provided a consent form describing the study with sufficient information for participants to make an informed decision regarding their participation. Participants must sign the IRB-approved informed consent form prior to participation in any study specific procedure. The participant must receive a copy of the signed and dated consent document. The original signed copy of the consent document must be retained in the medical record or research file.

Changes in the Protocol

Once the protocol has been approved by the UCSF Committee on Human Research (CHR), any changes to the protocol must be documented in the form of an amendment. The amendment must be signed by the Investigator and approved by PRC and the CHR prior to implementation. If it becomes necessary to alter the protocol to eliminate an immediate hazard to patients, an amendment may be implemented prior to CHR approval. In this circumstance, however, the Investigator must then notify the CHR in writing within five (5) working days after implementation.

Handling and Documentation of Clinical Supplies

The Investigator shall maintain complete records showing the receipt, dispensation, return, or other disposition of all investigational drugs. The date, quantity and batch or code number of the

drug, and the identification of patients to whom study drug has been dispensed by patient number and initials will be included.

The Investigator shall not make the investigational drug available to any individuals other than to qualified study patients. Furthermore, the Investigator will not allow the investigational drug to be used in any manner other than that specified in this protocol.

Case Report Forms (CRFs)

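### The 28-day capsule supply can run out before the latest permitted PK visit, so an adherent man sampled on Days 30 to 35 may give a washout value, not a trough (minor)

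*Combined protocol and SAP*

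**What the plan says.** **Supply.** Section 6.1, footnote k, sets six capsules a day and "168 capsules dispensed every 4 weeks during study visits". Section 7.1 agrees: "A 28 day supply of study drug will be provided to patients at each study visit every 4 weeks". No section provides for overage or interim resupply, and none forbids it.

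**Sample.** Section 6.3.5 states: "Serum itraconazole and hydroxy-itraconazole levels will be measured at the day 28 (+/- 7 days) study visit". The schedule in Section 6.1 shows no other PK draw and makes this visit the next dispensing point. Section 9.4 asks for a trough before the morning dose: "Patients should hold their morning dose until the collection is completed". It adds: "The actual day and time of collection will be recorded". It also has the protocol day written on the tube. It does not ask for the time of the last dose or set a maximum interval since that dose.

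**Kinetics.** Section 7.1 gives the oral half-life of itraconazole as "Single dose: ~21 hours, steady state: 64 hours". No half-life is given for hydroxy-itraconazole.

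**Analysis.** Section 10.7.2 lists the mean steady-state trough of drug and metabolite as a secondary endpoint. Section 10.8.2 summarises it by mean, SD and range, with no rule for a sample taken off drug. Section 5.3.2.3 plans to relate drug levels to PSA outcome.

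**Records.** Section 12.0 requires drug accountability: "The Investigator shall maintain complete records showing the receipt, dispensation, return, or other disposition of all investigational drugs".

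**The concern.** The supply has no slack, but the visit that replenishes it may be up to a week late. Sample and resupply fall at the same visit, so whatever delays one delays the other. A man can take every dose, attend within the window and still have no drug left when his trough is drawn. The instruction to hold the morning dose presumes that he has one to hold.

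The error runs one way, downward. It could lower the reported mean and set the low end of the range. It would also put falsely low exposure values into the planned comparison of drug level with PSA outcome. Each man has a single PK sample, so no later value can correct it.

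Other week-4 samples share the window. Hormones are drawn at day 28 with the same seven-day allowance (Section 6.3.5), and so is the optional skin biopsy for GLI1 (Section 6.3.6). These too would reflect a man off drug.

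**Working it through.** **Inputs.** Six capsules a day in two doses of three, and 168 per visit (6.1, 7.1). Day 1 is the first treatment day (6.3). The PK window is day 28 plus or minus 7, that is Days 21 to 35, or 15 days (6.3.5). The half-life is 64 h at steady state (7.1).

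**Step 1: the plan's figure.** 6 x 28 = 168, so the stated supply is reproduced exactly, with nothing over. 168 / 3 = 56 doses.

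**Step 2: when the supply ends.** With a morning first dose on Day 1, dose 56 falls on the evening of Day 28. The last true 12-hour trough is the morning of Day 29. A morning sample on Day D is then 24 x (D - 29) hours past that trough.

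**Step 3: level remaining.** Fraction of true trough = 2^(-hours past trough / 64).

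| Sample day | Hours past true trough | Fraction of true trough |
|---|---|---|
| 21 to 29 | 0 | 100% |
| 30 | 24 | 77% |
| 31 | 48 | 59% |
| 32 | 72 | 46% |
| 33 | 96 | 35% |
| 34 | 120 | 27% |
| 35 | 144 | 21% |

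Summing 56 twelve-hourly doses at a 64 h half-life also gives 0.210 for Day 35. Six of the 15 permitted days carry at least one full off-drug day. That is a count of days, not a probability.

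**Step 4: sensitivity of the Day 35 figure.**
- Evening first dose: the last dose is on the morning of Day 29, so 2^(-132/64) = 24%.
- Whole bottles of 30: 6 x 30 = 180 capsules, or 30 days, so 2^(-96/64) = 35%.
- Cycle 2 Day 1 read as Day 29, plus 7 = Day 36: 2^(-168/64) = 16%. Section 6.3.5 ends the PK window at Day 35, so this reading is not used.
- The 21 h single-dose half-life: 2^(-144/21) = about 1%. This is an extreme, since the men would be at steady state.

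**Step 5: the mean.** If a share f of men is late, and their true troughs are on average like the others', the mean is too low by f x (1 - fraction remaining). The documents do not give f, so both shares below are assumptions.

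| Assumed share late | All on Day 30 | Spread evenly over Days 30 to 35 | All on Day 35 |
|---|---|---|---|
| 10% (4 of 40) | 2.3% | 5.6% | 7.9% |
| 30% (12 of 40) | 6.9% | 16.7% | 23.7% |

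The even spread uses the average fraction remaining over Days 30 to 35, 0.443.

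**Step 6: does the fix close the gap?** With 210 capsules (35 days) at Day 1 and 168 (28 days) at each later visit, the supply after k dispensings is 35 + 28(k - 1) = 28k + 7 days. That covers a next visit seven days late, at every cycle. Enumerating all visit-day combinations for Cycles 2 to 5 gives no gap. Peak stock is 42 days, which the present rule can already reach when a late visit is followed by an early one.

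**The case against.** **This is the edge of the window.** The 21% needs the last permitted day, a morning start, full adherence, no hold, no spare capsules and an exact count of 168 from bottles of 30. Nine of the 15 permitted days show no gap. All of this stands. A reader might infer that late samples typically sit near 21%, or that the reported mean is off by about a quarter. The documents support neither. The larger figure requires 12 of 40 men to be late and every one of them to come on Day 35.

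**Silence is not prohibition.** A site could resupply early or round up to whole bottles. That is true, but the plan states an exact count, and even whole bottles leave Day 35 at about 35%. Leftover capsules also shrink the gap. For a grade 2 drug-related event, for instance, Section 8.3 says "treatment will be interrupted until the adverse event resolves to grade" reaches 1 or lower.

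**The half-life is uncertain.** Section 7.1 says that metabolism may saturate with repeated dosing, so decline could quicken as levels fall. That would lower the fraction remaining, so it does not rescue the sample.

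**Late samples can be found.** This largely stands. The protocol day on the tube identifies every sample from Days 30 to 35, and dispensing records show when supply could have run out. Neither shows when the last dose was taken, and Section 10.8.2 does not call for the check. The case report forms are not in the documents and may collect it.

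**An off-drug level is not a steady-state trough by definition.** An analyst might exclude it on that ground, but the plan leaves that to judgement after the data are seen.

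**Conclusion.** The point holds as a minor one. Followed exactly, the stated supply lets an adherent man with no leftover capsules or resupply be sampled 1 to 6 days past his true trough on Days 30 to 35. He would then be at about 77% down to a worst case of about 21% of his itraconazole trough, assuming first-order decline at 64 h. Days 21 to 29 are unaffected. The bias in the mean cannot be stated without the share of late visits, and nothing can be computed for hydroxy-itraconazole.

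What is touched is the descriptive secondary PK summary, the exploratory link between exposure and PSA, and the week-4 GLI1 and hormone samples. The size of the effect on those last two cannot be worked out from the documents.

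A reader might go on to infer that the gap threatens the 12-week PSA endpoint. The documents do not support that. They give no relation between a few days off drug and PSA decline, and the enumeration over Cycles 2 to 5 puts the largest cumulative gap at 7 days. No test or stopping rule uses the PK results.

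**What to change.** 1. Sections 6.1 and 7.1: dispense 210 capsules (seven bottles of 30) at Day 1 and 168 at each later visit, less capsules left over from a hold or dose reduction. Do not net off the seven-day reserve itself, or the gap returns.
2. Section 9.4: record the date and time of the last dose with the PK sample.
3. Section 10.8.2: base the steady-state trough summary on samples taken about 12 h after the last dose. List off-drug samples separately with days since last dose, and show an all-samples summary alongside.
4. If the supply rule cannot change, draw the PK sample by Day 29 and flag later samples from the protocol day on the tube.

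I would not add a separate rule setting aside men recently held or dose-reduced. It goes beyond the supply problem and would tilt the mean towards men who tolerate the drug.

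The cost is 210 - 168 = 42 extra capsules per patient, once, plus a capsule count at visits, one case report form field and a few sentences of analysis text. The main mean may lose a few samples, which the all-samples summary makes visible.
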